5.4 Randomisation

Participants will be randomised in a 1:1 ratio via a web-based randomisation system embedded within a trial database administered by the AKTN (Australian, New Zealand, and Canadian centres) or the Cambridge Clinical Trials Unit (UK centres). The systems will be accessible by centre staff via a password-protected encrypted website interface. Randomisation will be stratified by centre and use random permuted blocks to ensure similar numbers of participants in the two intervention groups at each centre.

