7. STATISTICAL CONSIDERATIONS

7.1 Sample size calculation

A sample size of 3,564 participants was calculated on the basis of the following assumptions: an annual rate of the primary outcome of 13% in the liberalised phosphate control group, a three year recruitment period, a five year total study duration, and 1% loss to follow-up. A two-sided log-rank test with an overall sample size of 3,564 participants has 80% power at the 5% significance level to detect a hazard ratio (HR) of 0.85 (a 15% intervention effect). The overall number of primary outcome events required is 1,190. A sample size of 3,564 participants has more than 90% power to detect a larger 20% intervention effect (HR 0.80). Therefore, the trial aims to enrol 3,600 participants.

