7.2 Statistical analysis

The intervention effect for the primary composite outcome will be illustrated by Kaplan–Meier product-limit estimates of the event-free survival time and analysed using a two-sided log-rank test stratified by country (Australia, Canada, New Zealand, and UK). Hazard ratios and corresponding 95% confidence intervals for the intervention effect adjusted for country will be calculated from a Cox proportional-hazards regression model. Intervention group differences according to major subgroups at randomisation (age, gender, country, race, diabetes, cardiovascular disease, time on dialysis) will be examined in Cox regression models incorporating an intervention group by subgroup variable interaction. The intervention effect for time-to-event secondary outcomes will be analysed using the same methods. Intervention groups will be compared on quality of life (EQ-5D-5L) scores using a linear mixed model. If there is substantial censoring due to transplantation and/or death, a joint modelling approach will be used accommodate the informative dropout.

Interim analyses on the primary outcome will be conducted using O'Brien-Fleming boundaries. There will be three interims and a final analysis. The interim analyses will be done when approximately 25%, 50% and 75% of the required events have occurred.

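### The 80% power in section 7.1 is the single-look figure; with the four O'Brien-Fleming looks in section 7.2, 1,190 events give about 79% (minor)

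*Protocol*

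**What the plan says.** Section 7.1 (Sample size calculation) bases the design on a single two-sided log-rank comparison of 3,564 people, which it says "has 80% power at the 5% significance level to detect a hazard ratio (HR) of 0.85 (a 15% intervention effect". On the event target it states: "The overall number of primary outcome events required is 1,190". It also claims more than 90% power at HR 0.80 and rounds the enrolment target up to 3,600. It mentions neither interim analyses nor an inflation factor.

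Section 7.2 (Statistical analysis) then sets out repeated testing of the same outcome: "Interim analyses on the primary outcome will be conducted using O'Brien-Fleming boundaries. There will be three interims and a final analysis". The interims fall at about 25%, 50% and 75% of the required events.

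Sections 2 (Study Overview) and 5.6 (Duration of follow up) end follow-up when 1,190 events have occurred.

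**The concern.** A group-sequential plan that holds the overall two-sided error at 5% uses some of that error at the interims. The final critical value must then be somewhat above 1.96, and for a fixed maximum number of events the overall power is somewhat below that of a single test. If the event target was calculated for a single test and not inflated, the stated power belongs to a design that the trial will not run.

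The spare enrolment might seem to cover this. It does not, because the trial is event-driven. Under the protocol's own assumptions, 36 more participants bring the 1,190th event forward, but the analysis still rests on 1,190 events.

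What is at stake is the accuracy of a headline design figure. The conduct of the trial is not affected.

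**Working it through.** **Inputs.** HR 0.85, two-sided 5%, 80% power and 1,190 events (section 7.1). Allocation: "Participants will be randomised in a 1:1 ratio" (section 5.4). Control rate: "an annual rate of the primary outcome of 13% in the liberalised phosphate control group" (section 7.1). Timing and loss: "a three year recruitment period, a five year total study duration, and 1% loss to follow-up" (section 7.1). Looks at 25%, 50%, 75% and 100% of events with O'Brien-Fleming boundaries (section 7.2).

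**Step 1: reproduce the event count as a single-look design.** Schoenfeld, 1:1 allocation:

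d = 4(z₀.₉₇₅ + z₀.₈₀)² / (ln HR)² = 4(1.960 + 0.842)² / (ln 0.85)² = 1,188.7, so 1,189 events.

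Freedman's formula gives 1,194. At 1,190 events the drift is √(1190/4) × |ln 0.85| = 17.248 × 0.16252 = 2.803, and single-look power is Φ(2.803 − 1.960) = 80.04%. The stated 1,190 is therefore the uninflated count.

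**Step 2: reproduce the sample size.** Assume exponential survival, uniform accrual over R = 3 years, total duration T = 5 years, and the 1% loss read as a hazard of η = 0.01 per year. The section does not say per year, but this reading reproduces its figure. The event probability in an arm with hazard λ, writing h = λ + η, is

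p = (λ/h) × [1 − (e^(−h(T−R)) − e^(−hT)) / (hR)].

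- Control, λ = 0.13: p = 0.3555.
- Intensive, λ = 0.85 × 0.13 = 0.1105: p = 0.3123.
- Mean: 0.3339. N = 1,190 / 0.3339 = 3,564.

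This matches section 7.1 exactly, so no interim allowance entered through N either.

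**Step 3: apply the plan in section 7.2.** Recursive numerical integration for four equally spaced looks, symmetric two-sided boundaries, overall two-sided alpha 5%, drift 2.803 at 1,190 events:

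| | Classical O'Brien-Fleming | Lan-DeMets, O'Brien-Fleming type |
|---|---|---|
| Boundaries, abs(Z) | 4.049, 2.863, 2.337, 2.024 | 4.333, 2.963, 2.359, 2.014 |
| Final nominal two-sided p | 0.0429 | 0.0440 |
| Overall power, HR 0.85 | 79.1% | 79.3% |
| Overall power, HR 0.80 | 96.8% | 96.8% |
| Inflation factor for 80% power | 1.024 | 1.020 |
| Events for 80% power | about 1,217 | about 1,212 |

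The power figures count rejections at any of the four looks. Taking only a single test at the final boundary would give Φ(2.803 − 2.024) = 78.2% and understate the power, because it leaves out trials that cross an interim boundary but would miss the final one.

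**Step 4: size of the gap.** 80.0 − 79.1 = 0.9 percentage points (0.7 with Lan-DeMets). In events, the gap is 1,217 − 1,190 = 27, or 1,212 − 1,190 = 22, about 2% of the target.

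**Step 5: does enrolling 3,600 close it?** With the Step 2 assumptions, 3,600 participants would yield 3,600 × 0.3339 ≈ 1,202 events by year 5. But follow-up closes at 1,190, so the power stays as in Step 3.

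**The case against.** The strongest objection is that the gap is trivial. It is under one power point. At 1,190 events the four-look design has 80% power at about HR 0.848 instead of 0.850, and the choice between Schoenfeld and Freedman alone moves the target by 5 events. No decision about the trial depends on it. This stands, and it is why the point is only minor. It does not make the sentence right: under the plan in section 7.2 with an overall 5%, 1,190 events do not give 80%.

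A second objection is that the statistical analysis plan, which is not at hand, will deal with the interims. It can set the boundary version, the final nominal level (about 0.043), recalculation from the actual event fractions, and any interval matched to the boundary. Their absence from the protocol is no fault. It cannot, however, make 1,190 events deliver the stated 80% under these looks.

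Three stronger readings are tempting, and the protocol supports none of them.

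- *Sections 7.1 and 7.2 use conflicting alphas.* The ordinary joint reading is an overall 5% spread over four looks. Section 7.1 nowhere says that the final look is tested at a nominal 5%.
- *The type I error is inflated to about 5.6%.* That figure arises only if 1.96 is used at the final look after the O'Brien-Fleming interims. The protocol does not plan this, and section 7.2 points the other way.
- *The 95% interval contradicts the decision.* Section 7.2 says "Hazard ratios and corresponding 95% confidence intervals for the intervention effect adjusted for country will be calculated from a Cox proportional-hazards regression model", but that is the effect estimate. The primary outcome is analysed with the stratified log-rank test, and nothing makes the interval decide significance. The two could differ only for an observed HR between about 0.889 and 0.893. Counting only trials that reach the final look, the chance of that is about 1.6% at a true HR of 0.85 and 0.6% under the null. A conventional 95% interval beside a group-sequential test is not an error.

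**Conclusion.** The stated 80% power is slightly too high for the design as planned. It is correct for a single analysis, but about 79% (79.1% to 79.3%, depending on the boundary version) for the four-look plan. The claim of more than 90% at HR 0.80 is unaffected. The point is minor and confined to one figure in section 7.1.

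The result assumes proportional hazards, 1:1 allocation, looks exactly at the planned fractions, an overall two-sided alpha of 5%, and stopping for efficacy only. Section 9.4 names efficacy stopping, and the protocol states no futility rule.

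**What to change.** In section 7.1, tie the power to the plan in section 7.2, for example: *With three interim analyses and a final analysis under O'Brien-Fleming boundaries and an overall two-sided alpha of 5%, 1,190 events give about 79% power to detect a hazard ratio of 0.85.* The sentence on HR 0.80 can stay.

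The cost is one sentence and a quoted power about one point lower. Event target, enrolment and conduct do not change, and no extra patients are needed. If the trial committee prefers to keep 80%, the alternative is an event target of about 1,217 (about 1,212 with Lan-DeMets spending). That exceeds the roughly 1,202 events expected by year 5 from 3,600 participants, so it would mean somewhat longer follow-up or a slightly larger sample. For a gap of this size, restating the power is the proportionate choice.

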7.2 Statistical analysis

The intervention effect for the primary composite outcome will be illustrated by Kaplan–Meier product-limit estimates of the event-free survival time and analysed using a two-sided log-rank test stratified by country (Australia, Canada, New Zealand, and UK). Hazard ratios and corresponding 95% confidence intervals for the intervention effect adjusted for country will be calculated from a Cox proportional-hazards regression model. Intervention group differences according to major subgroups at randomisation (age, gender, country, race, diabetes, cardiovascular disease, time on dialysis) will be examined in Cox regression models incorporating an intervention group by subgroup variable interaction. The intervention effect for time-to-event secondary outcomes will be analysed using the same methods. Intervention groups will be compared on quality of life (EQ-5D-5L) scores using a linear mixed model. If there is substantial censoring due to transplantation and/or death, a joint modelling approach will be used accommodate the informative dropout.

Interim analyses on the primary outcome will be conducted using O'Brien-Fleming boundaries. There will be three interims and a final analysis. The interim analyses will be done when approximately 25%, 50% and 75% of the required events have occurred.

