2. STUDY OVERVIEW

Hyperphosphataemia is highly prevalent in patients with end-stage kidney disease (ESKD) and associated with increased mortality risk. The Kidney Disease: Improving Global Outcomes (KDIGO) Clinical Practice Guidelines for chronic kidney disease–mineral and bone disorder (CKD-MBD) *suggest* lowering elevated phosphate levels towards the normal range (level 2C suggestion)^{1,2}. However, trial data demonstrating that treatments that lower serum phosphate prevent patient-centred outcomes are lacking^{1,2}.

The primary objective of the Pragmatic randomised trial of High Or Standard PHosphAte Targets in End-stage kidney disease (PHOSPHATE Study) is to test the hypothesis that phosphate-lowering treatment to reduce serum phosphate level towards the normal level (≤ 1.5 mmol/L) reduces fatal and non-fatal major cardiovascular events in patients receiving dialysis compared to a strategy of liberalised phosphate control with phosphate-lowering treatment for serum phosphate levels ≤ 2.5 mmol/L.

The PHOSPHATE Study is an investigator-initiated, international, multi-centre, prospective, randomised, open-label, parallel-group, superiority, and pragmatic large simple trial (LST). A total of 3600 adult participants (≥ 45 years or ≥ 18 years with diabetes) with ESKD receiving haemodialysis or peritoneal dialysis for at least 3 months and who are prescribed at least one phosphate lowering medication will be recruited from renal units in Australia, New Zealand, Canada and the UK.

[figure not shown]
The primary outcome measure is time to a composite endpoint of cardiovascular death or non-fatal major cardiovascular event (myocardial infarction, coronary revascularisation, stroke or peripheral arterial event). The secondary outcome measures are (a) time to a composite of all-cause mortality, (b) individual components of the composite outcomes, (c) quality of life using EQ-5D-5L.

The participants will be randomised to either an intensive phosphate control - phosphate-lowering treatments aimed to intensively lower serum phosphate

concentration towards normal level (≤ 1.50 mmol/L) or to a strategy of liberalised phosphate control – which will be achieved by discontinuation of all phosphate-lowering medications and commence phosphate-lowering treatments only if serum phosphate concentration exceeds 2.50 mmol/L.

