3.1 Outcomes in ESKD patients receiving dialysis

Over three million people worldwide are currently living with ESKD and require renal replacement therapy^{3, 4}. The need for dialysis is projected to double globally by 2030. Although dialysis is a life-sustaining therapy, the death rate among ESKD patients receiving dialysis is unacceptably high at 13 per 100 person-years⁵. Despite the annual cost of more than \$34 billion in United States alone⁶, the age-adjusted mortality rates of dialysis patients is 10 to 100 times higher than that of the general population^{7, 8}. Furthermore, ESKD patients suffer from impaired taste, loss of appetite, malnutrition, and poor quality of life.⁹

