5.7.2 Secondary outcome measures

1. Individual components of the primary composite endpoint (cardiovascular death, non-fatal myocardial infarction, coronary revascularisation, non-fatal stroke and peripheral arterial event)
2. Time to all-cause death
3. All-cause hospitalisation
4. Quality of life measured using EQ-5D-5L

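### Kaplan–Meier curves for a composite that leaves out non-cardiovascular death overstate cumulative risk when read as risks; cumulative incidence curves should replace them

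*Protocol*

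**What the plan says.** Section 2 defines the endpoint: "The primary outcome measure is time to a composite endpoint of cardiovascular death or non-fatal major cardiovascular event". Section 5.7.1 lists five components, and death from a non-cardiovascular cause is not among them. Section 7.2 displays this endpoint by Kaplan–Meier "product-limit estimates of the event-free survival time and analysed using a two-sided log-rank test stratified by country", with a Cox model for the hazard ratio. It then adds: "The intervention effect for time-to-event secondary outcomes will be analysed using the same methods". Those secondary outcomes include the components one by one (section 5.7.2): "cardiovascular death, non-fatal myocardial infarction, coronary revascularisation, non-fatal stroke and peripheral arterial event".

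The only sentence in section 7.2 that treats death as a problem is "If there is substantial censoring due to transplantation and/or death, a joint modelling approach will be used accommodate the informative dropout". It follows directly on the EQ-5D-5L mixed model and concerns dropout from that model. No cumulative incidence function or other competing-risk method is named for any time-to-event outcome.

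On size, section 7.1 assumes "an annual rate of the primary outcome of 13% in the liberalised phosphate control group". Section 3.1 says that "the death rate among ESKD patients receiving dialysis is unacceptably high at 13 per 100 person-years", without splitting it into cardiovascular and other deaths.

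**The concern.** A patient who dies of a non-cardiovascular cause can no longer have a primary event. The protocol does not say in words that such deaths are censored, but this follows from the endpoint and the estimator together. One minus Kaplan–Meier then describes a setting in which nobody dies of anything else, and it is higher than the proportion of randomised patients who have the event. The same holds for cardiovascular death on its own, with other death competing. It also holds for each non-fatal component, with any death competing.

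Competing death is unlikely to be negligible here, because the all-cause death rate in section 3.1 is as high as the assumed primary event rate. What is at stake is the descriptive side of the main result: the risks a reader takes off the published curves, and any absolute difference worked out from them.

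**Working it through.** **Inputs.** From section 7.1: control rate 13% per year, hazard ratio 0.85, 3-year recruitment, 5-year total duration, 1% loss, 1,190 events, 3,564 participants. Potential follow-up therefore runs from 2 to 5 years, with a mean of 3.5. Assumption: the non-cardiovascular death rate *m* is not in the protocol. I take 3 to 10 per 100 person-years, with 6.5 (half of the 13 per 100 in section 3.1) as the middle value. The low end is close to the median all-cause rate of 3.0 that section 3.4.1 reports for earlier trials and itself calls low-risk.

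**Step 1: reproduce the plan's figures, to fix how the 13% is to be read.** Events by Schoenfeld: 4 × (1.960 + 0.842)² / (ln 0.85)² = 1,189 (stated 1,190). With exponential hazards 0.13 and 0.13 × 0.85 = 0.1105, uniform accrual and 1% loss per year, the mean event probability is 0.3339, and 1,190 / 0.3339 is about 3,565 (stated 3,564). Reading 13% as an annual probability (hazard 0.139) gives 3,376, which does not match. The plan therefore used a hazard of 0.13.

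**Step 2: the composite, control arm.** With constant hazards *l* and *m*:

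- 1 − KM = 1 − exp(−*l t*)
- cumulative incidence = *l*/(*l*+*m*) × [1 − exp(−(*l*+*m*) *t*)]

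Example at 5 years with *m* = 0.065: 1 − exp(−0.65) = 47.8%, against (0.13/0.195) × [1 − exp(−0.975)] = 41.5%.

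| Years | 1 − KM | Cumulative incidence, *m* = 0.03 / 0.065 / 0.10 | Excess (points) |
|---|---|---|---|
| 2 | 22.9% | 22.3 / 21.5 / 20.8% | 0.6 / 1.4 / 2.1 |
| 3.5 | 36.6% | 34.8 / 33.0 / 31.3% | 1.7 / 3.6 / 5.3 |
| 5 | 47.8% | 44.7 / 41.5 / 38.6% | 3.1 / 6.3 / 9.2 |

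(Differences here and below are taken before rounding.)

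**Step 3: the difference between arms, *m* = 0.065 in both.** For the intensive arm (*l* = 0.1105), 1 − KM is 32.1% at 3.5 years and 42.4% at 5 years. Cumulative incidence is 28.9% and 36.8%. The absolute difference is therefore 4.5 points by Kaplan–Meier against 4.1 at 3.5 years, and 5.3 against 4.7 at 5 years. Most of the excess cancels.

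**Step 4: the components (rates assumed).** For a non-fatal component at 1 to 3 per 100 person-years with all death competing at 13 per 100, the excess is 0.7 to 1.9 points at 3.5 years (for example 10.0% against 8.0% at 3 per 100) and 1.3 to 3.6 points at 5 years. For cardiovascular death at 6.5 per 100 with other death at 6.5 per 100, it is 2.1 and 3.8 points.

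**Step 5: what the curve's label would convey.** At 5 years with *m* = 0.065, the control curve reads 100 − 47.8 = 52.2% event-free survival. The proportion alive without an event would be exp(−0.975) = 37.7%. The proportion without a primary event, dead or alive, would be 100 − 41.5 = 58.5%. The plotted figure is neither.

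**The case against.** The strongest reply is that the protocol commits to no absolute risks. Kaplan–Meier is there to illustrate; the inference is the log-rank test and the Cox hazard ratio. No risk difference or number needed to treat is promised, and the statistical analysis plan, which is not at hand, could add cumulative incidence curves. This stands as a limit: the error arises only where the curves are read or reported as risks. It does not dispose of the point, because section 7.2 names a specific estimator rather than leaving the choice open, and readers commonly take risks from the main figure.

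The size is also conditional. The non-cardiovascular rate is assumed, section 5.2.2 excludes patients likely to die within 6 months, and only the earliest recruits reach 5 years. That stands, and is why the range and the earlier time points are shown.

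Three stronger readings are tempting, and the protocol does not support them:

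- **Every reported risk will be several points too high.** For non-fatal components at the assumed rates, the excess at mean follow-up is under 2 points.
- **The primary test is compromised.** Log-rank and Cox remain valid for the cause-specific hazard, and power follows from the event count.
- **The non-fatal components could mislead on direction, so myocardial infarction and stroke should be redefined as fatal or non-fatal.** A shift from non-fatal to fatal events would appear in cardiovascular death and all-cause death, both prespecified, and both forms count in the composite. Redefinition would change secondary endpoints and needs deaths attributed to infarction or stroke, which the protocol does not show being collected.

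**Conclusion.** The point holds as one about display and description. Kaplan–Meier is the wrong estimator for the cumulative risk of this composite and its components, and the joint-model sentence does not repair that. The direction is certain whenever deaths outside the endpoint occur. The size depends on the assumed rate: at mean follow-up the control-arm excess for the composite is most plausibly a few points (3.6 at 6.5 per 100). It is small at 2 years and larger at 5, while the between-arm difference moves by roughly half a point. These figures assume constant hazards and the same non-cardiovascular death rate in both arms. All-cause death is unaffected, as are the log-rank test, the hazard ratio, the 1,190-event target and the power. The change is worth making because it is cheap, not because the trial's main conclusion is at risk.

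**What to change.** In section 7.2, keep the stratified log-rank test and the Cox model, and describe both as cause-specific analyses. Replace the Kaplan–Meier display for the primary composite and its components by Aalen–Johansen cumulative incidence curves:

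- for the composite and for cardiovascular death, non-cardiovascular death is the competing event;
- for the non-fatal components, death from any cause is the competing event;
- for all-cause death, Kaplan–Meier stays.

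Take any absolute risk or risk difference that is reported from these curves. Leave the definitions of the myocardial infarction and stroke components as they are.

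The cost is a change of wording and a little more analysis work. Table 6.1 already schedules primary endpoints and all-cause death every 3 months, so deaths outside the composite can be identified without new data. No participants, events or alpha are needed. The downside is that absolute differences will look slightly smaller than on the Kaplan–Meier scale.

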6.6 Clinical assessment

6.6.1 Baseline demographic characteristics

Date of birth

Sex

Height and weight

Race/Ethnicity

Medical history (diabetes mellitus, myocardial infarction, coronary artery disease, heart failure, stroke, peripheral arterial disease, cancer, parathyroidectomy, calciphylaxis)

Primary cause of kidney disease

Smoking history

Key concomitant medication – phosphate-lowering medication, calcium, nutritional vitamin D, active vitamin D (calcitriol), cinacalcet.

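### The primary analysis is fixed to adjust for country alone, forgoing the modest power that pre-specified adjustment for age, diabetes and cardiovascular history could add

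*Protocol*

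**What the plan says.** Section 7.2 fixes both parts of the primary analysis. The outcome is to be "analysed using a two-sided log-rank test stratified by country (Australia, Canada, New Zealand, and UK"). For the estimate: "Hazard ratios and corresponding 95% confidence intervals for the intervention effect adjusted for country will be calculated from a Cox proportional-hazards regression model". No other covariate is named for either.

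Section 7.2 then lists the variables for interaction models: "major subgroups at randomisation (age, gender, country, race, diabetes, cardiovascular disease, time on dialysis"). Section 6.6.1 collects date of birth and "Medical history (diabetes mellitus, myocardial infarction, coronary artery disease, heart failure, stroke, peripheral arterial disease, cancer, parathyroidectomy, calciphylaxis").

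Section 5.4 sets the allocation: "Participants will be randomised in a 1:1 ratio", and "Randomisation will be stratified by centre and use random permuted blocks". Country is therefore a coarser grouping of the factor used in the randomisation.

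Section 7.1 sizes the trial on a two-sided log-rank test with no covariates, which "has 80% power at the 5% significance level to detect a hazard ratio (HR) of 0.85".

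**The concern.** In a proportional-hazards model, leaving out a covariate that predicts the outcome pulls the estimated treatment hazard ratio towards 1, even under perfect randomisation. The log-rank test loses power in the same way. Covariates that are measured before randomisation and named in advance can recover that loss.

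There is reason to expect these covariates to be prognostic here. The history items in section 6.6.1 (myocardial infarction, coronary disease, stroke, peripheral arterial disease) closely match the components of the primary composite in section 5.7.1. Section 5.2.1 admits people aged 45 or over, or 18 or over with diabetes, so wide variation in age and diabetes is built into the population.

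The adjustment set is written into the protocol, not left open. A later analysis plan that added covariates to the primary analysis would depart from section 7.2. Power is also not generous: 80% for a 15% reduction in hazard, with three interim looks to come out of it.

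**Working it through.** **1. The plan's own figures.** Inputs from section 7.1: HR 0.85, two-sided 5%, 80% power, control rate 13% per year, 3 years' recruitment, 5 years in total, 1% loss. The 1:1 ratio is from section 5.4.

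- Schoenfeld: events = 4(1.96 + 0.8416)² / (ln 0.85)² = 31.40 / 0.02641 = 1,189. Freedman: 7.849 × (1.85/0.15)² = 1,194. Stated: 1,190.
- Power at 1,190 events: Φ(0.1625 × √1,190 / 2 − 1.96) = 80.0%.
- Sample size: with exponential survival, uniform recruitment and loss read as 1% per year, the event probability is 0.3555 (control) and 0.3123 (intensive), mean 0.3339. Then 1,190 / 0.3339 gives about 3,565. Stated: 3,564.

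The design reproduces, so the country-only analysis does not undercut the stated power.

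**2. Interim looks.** Section 7.2 adds O'Brien-Fleming looks at about 25%, 50% and 75% of events. With four equally spaced looks the final critical value is about 2.025. Power at 1,190 events is then about 79.1%, and about 1,216 events would be needed for 80%.

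**3. Gain from adjustment.** The protocol gives no covariate hazard ratios, prevalences or number of centres, so the following are assumptions: 90 centres in four countries, balanced allocation within centre, and diabetes and cardiovascular history each present in 45%. Each scenario had 1,000 simulated trials of 3,564 participants, about 1,180 to 1,198 events, and a treatment HR of 0.85 given the covariates.

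The ratio r of mean Z (adjusted over country-only) was applied to the design value: power = Φ(2.8016 × r − 1.96). Equivalent events for 80% power = 1,190 / r².

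| Assumed effects (HR per SD of age; diabetes; CV history) | Mean \|Z\| country-only | Mean \|Z\| adjusted | r | Power if country-only is 80% | Equivalent events |
|---|---|---|---|---|---|
| None | 2.859 | 2.860 | 1.0003 | 80.0% | 1,189 |
| Modest (1.2; 1.3; 1.5) | 2.734 | 2.783 | 1.0179 | 81.4% | 1,148 |
| Moderate (1.3; 1.5; 2.0; centre SD 0.2) | 2.652 | 2.781 | 1.0486 | 83.6% | 1,082 |
| Strong (1.5; 1.8; 2.5; centre SD 0.3) | 2.474 | 2.713 | 1.0966 | 86.7% | 990 |

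Monte Carlo error is about 1.3 points on a simulated power, and smaller on the paired ratios.

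**4. Where the gain comes from.** The standard error of the log HR was about 0.058 with or without covariates, matching 2/√1,190 = 0.058. What moved was the estimate: 0.853 to 0.851 (modest), 0.857 to 0.850 (moderate), 0.866 to 0.853 (strong).

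**5. Centre in place of country, without covariates.** On the same scale, power was 79.3%, 79.3%, 79.9% and 80.2% across the four scenarios, a change of −0.8 to +0.2 points.

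**The case against.** The best defence is that nothing here is wrong. A country-stratified log-rank test with a minimally adjusted hazard ratio is a standard, valid primary analysis, and it matches the test on which section 7.1 sizes the trial. The gain depends on covariate effects that the protocol does not give, and with modest effects it is only about 1 point. Adjustment also changes what is estimated. All of this stands, and it makes the point an efficiency improvement and not an error. It does not remove the point, because the gain needs no new participants or data and the protocol wording closes it off.

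Three stronger readings are tempting and are not supported.

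- *The trial really has well under 80% power.* A simulation ending at about 1,000 to 1,030 events, with 0.85 taken as the covariate-conditional hazard ratio, gives the country-only analysis 67% to 71%. But section 5.6 continues follow-up to 1,190 events, and section 7.1 applies 0.85 to the log-rank test itself. At 1,015 events the Schoenfeld formula alone gives only 73.5%, so much of that shortfall is too few events.
- *Ignoring centre costs power or invalidates the test.* Centre stratification gave no material gain. Ignoring a balancing factor tends to make a test slightly conservative and does not inflate type I error. Centres may also be small: section 3.5.1 reports eight New Zealand units supporting 100 participants, about 12 each, or roughly 4 events per unit at a probability of 0.33.
- *Adjustment is free.* The hazard ratio becomes conditional, the covariates must be defined in advance, and missing values must be handled.

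**Conclusion.** The point holds as a recommendation on efficiency. Section 7.2 commits the primary test and estimate to country alone and leaves unused three baseline variables that the trial will hold. Relative to 80% power for the country-only test, pre-specified adjustment adds about 0 to 7 points: 0 with no prognostic effect, 1 modest, 4 moderate, 7 strong. At the strong end this equals a saving of about 200 events (1,190 − 990). With no prognostic effect the simulated loss was nil.

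The range rests on the assumed covariate effects, prevalences and centre structure, none of which the protocol supplies. The plan as written is valid and meets its stated power, apart from the roughly 1 point taken by the interim looks. The difference between the randomisation factor (centre) and the analysis factor (country) is a matter of consistency to be explained, not a source of lost power.

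**What to change.** Before unblinding, amend section 7.2 as follows.

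- State that the primary test and the primary hazard ratio, at each interim and at the final analysis, come from a Cox model stratified by country, with age (continuous), diabetes and history of cardiovascular disease as pre-specified covariates. The test must be named as well as the estimate: adding covariates to the Cox model alone leaves the power of the log-rank test unchanged.
- Define history of cardiovascular disease from the items in section 6.6.1.
- Give a simple rule for missing covariate values.
- Keep the country-stratified log-rank test and the country-only hazard ratio as supportive results.
- Use the same model for all-cause death.
- Optionally, add a centre-frailty or centre-stratified analysis as a sensitivity check that respects the randomisation.

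The cost is a protocol amendment and matching wording in the analysis plan. The primary hazard ratio becomes conditional on the covariates, and the gain shows as an estimate further from 1 with an unchanged standard error. Reporting the country-only hazard ratio beside it keeps the result comparable with the assumption in section 7.1.
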